7.5 Loss or Destruction of Samples/Data

Participants may decide at any point not to have their specimens or data stored. In this case, the samples or data will be destroyed after the participant has provided a written request to do so, which includes a description of which samples or data should be destroyed. Once the written request is received, the PI will have the applicable samples/data destroyed and report what was done to both the participant and to the IRB. This decision will not affect the individual's participation in this protocol or any other protocols at NIH.

Any loss or unanticipated destruction of samples or data that meets the NIH Intramural Protocol Deviation definition, or results in a deviation that compromises the scientific integrity of the data collected for the study will be reported to the NIEHS IRB.

8 Statistical Considerations

8.1 Data Analysis

Descriptive statistics will be used to characterize the sociodemographic, health, and lifestyle information of enrolled participants. Standard deviations, means, medians, and interquartile ranges will be used to summarize continuous variables. Rates and proportions will be estimated for discrete variables and bivariate relationships will be explored using cross tabulations. 95% confidence intervals (CIs) will be estimated where appropriate. Propensity score weighting or matching can be used in subsequent health effects analyses if the descriptive data indicate that the enrolled population is not representative of the target population.

Relationships between exposures or disaster-related activities and health outcomes can be investigated by fitting regression models. Logistic regression models can be used for dichotomous outcomes to estimate odds ratios (ORs) and 95% confidence intervals (CIs) for each exposure. Least squares regression can be used for continuous outcomes to estimate effect parameters and standard errors (SEs) for each exposure. Outcomes may include a range of doctor-diagnosed general and physical health outcomes, clinical measurements of health status (e.g. pulmonary or neurobehavioral function), and self-reported health status and disease-related symptoms. Relevant demographic variables (e.g., gender, age, race, socioeconomic status indicators) and other exposures will be included in the regression models as covariates and effect modifiers. Various refinements to these basic methods, as well as additional analytical approaches, will also be pursued as appropriate. Stratified analyses will be used when there is evidence of effect modification (interaction), i.e., when

the exposure-health outcome associations differ across levels of a covariate (e.g., SES, age, etc.)

8.2 Sample Size

This study is designed not around a few narrow *a priori* hypotheses, but rather to allow the investigation of a wide range of potential adverse exposure scenarios and related health effects. Thus, a wide range of exposure scenarios and possible health effects is considered in the power analysis. We anticipate enrolling disaster response workers deployed to a federally declared disaster area to conduct emergency response activities where a portion of the workers will experience a given exposure. The study size and the number of individuals who are exposed – and the statistical power – will largely be determined by the number of individuals impacted by the disaster. For dichotomous health outcomes, **Table 3** presents minimum detectable odds ratios across a range of proportions of workers with “high” exposure and a range of proportions of workers with “low” exposure (the referent group). Given that all participants will be workers and the types and levels of exposure will vary by the type of disaster and type of job, “high” exposure and “low” exposure (referent group) will be determined in the context of the individual studies. This may be based on established cut points or, in the absence of established scientific or clinical guidelines, on quartiles (e.g. highest vs. lowest quartile). The power analysis in **Table 3** is based on an α of 0.05, power of 80%, and a two-sided Pearson chi-square test for two proportions, which is likely to be more conservative than a logistic regression analysis including covariates.

Table 3 Minimum detectable odds ratio for dichotomous health outcomes for a range of proportions of participants with “high” exposure in the disaster and a range of proportions of health outcomes among participants in the referent group. N is the total number of participants.

Proportion in Referent Group with Health Outcome	Proportion of Sample with “High” Exposure	Minimum Detectable Odds Ratio (OR)					
		N =250	N =500	N = 1,000	N = 2,000	N = 5,000	N = 10,000
3%	5%	10.65	6.56	4.44	3.21	2.27	1.86
	10%	7.14	4.71	3.34	2.52	1.89	1.61
	25%	4.99	3.43	2.55	2.02	1.60	1.41
	50%	4.58	3.17	2.37	1.89	1.53	1.36
	75%	5.78	3.81	2.73	2.10	1.63	1.43
	90%	10.08	6.06	3.96	2.81	2.00	1.66
5%	5%	8.19	5.15	3.59	2.67	1.97	1.66
	10%	5.51	3.76	2.76	2.16	1.68	1.47
	25%	3.90	2.80	2.17	1.77	1.46	1.32
	50%	3.55	2.58	2.02	1.68	1.40	1.28
	75%	4.33	3.01	2.26	1.82	1.48	1.33
	90%	7.16	4.52	3.11	2.32	1.74	1.50
10%	5%	6.13	3.94	2.83	2.19	1.70	1.47
	10%	4.14	2.93	2.24	1.82	1.49	1.34
	25%	2.97	2.25	1.82	1.55	1.33	1.23
	50%	2.71	2.08	1.71	1.47	1.29	1.20
	75%	3.16	2.34	1.86	1.57	1.34	1.23
	90%	4.86	3.27	2.40	1.89	1.52	1.35
30%	5%	5.09	3.12	2.26	1.80	1.46	1.31
	10%	3.24	2.32	1.83	1.54	1.32	1.22
	25%	2.31	1.82	1.53	1.36	1.22	1.15
	50%	2.08	1.69	1.45	1.31	1.19	1.13
	75%	2.33	1.83	1.54	1.36	1.22	1.15
	90%	3.32	2.37	1.86	1.56	1.33	1.22

When the sample size is relatively large (≥ 2000), odds ratios of less than 2.00 can be detected, except when the health outcomes are rare and the proportion of participants in the “high” exposure group is very small or very large. In general, larger sample sizes are required for health outcomes that are rare, while smaller sample sizes are adequate for health outcomes with a higher prevalence, especially when the sample sizes are balanced between the exposed and referent groups.

For continuous health outcomes, **Table 4** presents minimum detectable mean differences, in standard deviations, across a range of proportions of exposure among enrolled participants. The power analysis in **Table 4** is based on an α of 0.05, power of 80%, and a two-sided t-test, which is likely to be more conservative than a multivariate regression analysis including covariates.

Table 4. Minimum detectable mean differences, in standard deviations, for continuous health outcomes for a range of proportions of participants exposed in the disaster. N is the total number of participants.

Proportion of Total Sample with “High” Exposure	Minimum Detectable Mean Difference					
	N = 250	N = 500	N = 1,000	N = 2,000	N = 5,000	N =10,000
5%	0.83	0.58	0.41	0.29	0.18	0.13
10%	0.59	0.42	0.30	0.21	0.13	0.09
25%	0.41	0.29	0.21	0.15	0.09	0.06
50%	0.36	0.25	0.18	0.13	0.08	0.06
75%	0.41	0.29	0.21	0.15	0.09	0.06
90%	0.59	0.42	0.30	0.29	0.13	0.09

When the sample size is relatively large (≥ 1000), then a study has power to detect mean differences of 0.5 standard deviations or smaller. The smallest minimum detectable mean differences occur when the sample sizes are balanced between the “high” exposure and the referent groups.

9 Protection of Human Subjects

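### Protocol section 8.2 has one wrong cell in Table 4 (90% exposed, N = 2,000: 0.29 SD printed, 0.21 SD correct) and a summary sentence after Table 3 whose exception misses three cells (minor)

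*Protocol*

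**What the plan says.** Protocol section 8.2 fixes no sample size. It tabulates what could be detected for six totals, from N = 250 to N = 10,000. The Protocol Summary says that such estimates will guide the enrolment target.

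**Table 4 (continuous outcomes).** The table "presents minimum detectable mean differences, in standard deviations, across a range of proportions of exposure among enrolled participants". It "is based on an α of 0.05, power of 80%, and a two-sided t-test". Three of its rows matter here:

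- 5% exposed: "5% 0.83 0.58 0.41 0.29 0.18 0.13"
- 10% exposed: "10% 0.59 0.42 0.30 0.21 0.13 0.09"
- 90% exposed: "90% 0.59 0.42 0.30 0.29 0.13 0.09"

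The text below the table concludes that from N = 1,000 upwards, differences of half a standard deviation or smaller can be detected.

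**Table 3 (dichotomous outcomes).** The calculation "is based on an α of 0.05, power of 80%, and a two-sided Pearson chi-square test for two proportions". The text below it says: "When the sample size is relatively large (≥ 2000), odds ratios of less than 2.00 can be detected". The same sentence goes on to exempt situations in which the outcome is rare and, at the same time, the highly exposed fraction is very small or very large. None of these three terms is defined. One of the 3%-outcome rows, for 75% exposed, reads "75% 5.78 3.81 2.73 2.10 1.63 1.43".

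**The concern.** With a common standard deviation, the detectable mean difference depends on the two group sizes only through 1/n₁ + 1/n₀. Exchanging the groups changes nothing, so the 10% and 90% rows of Table 4 must be identical. They agree in five of six columns and differ at N = 2,000. The 90% row also looks wrong on its own: it falls only from 0.30 to 0.29 when N doubles from 1,000 to 2,000, where a reduction by a factor of √2 is expected.

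In the sentence after Table 3, the two conditions of the exception are joined by 'and'. Some N = 2,000 cells at or above 2.00 meet only one of them.

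What is at stake is modest but practical. The target is to be set by an expedited amendment once a disaster has occurred, and these tables are what the team would consult. Section 8.2 also names quartiles as a fallback for defining exposure groups, so a 25% exposed share is not an exotic case.

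**Working it through.** **Table 4**

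Inputs, all from section 8.2: two-sided α 0.05, power 80%, SD = 1, N = 2,000. With 90% exposed, n₁ = 1,800 and n₀ = 200.

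Formula: d = (z₀.₉₇₅ + z₀.₈₀) × √(1/n₁ + 1/n₀), with z₀.₉₇₅ + z₀.₈₀ = 1.960 + 0.842 = 2.802.

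1. Reproduce neighbouring figures first.
   - 90% exposed, N = 1,000: 2.802 × √(1/900 + 1/100) = 0.295, printed 0.30.
   - 5% exposed, N = 2,000: 2.802 × √(1/100 + 1/1,900) = 0.287, printed 0.29.
2. The disputed cell: √(1/1,800 + 1/200) = 0.0745, and 2.802 × 0.0745 = 0.2088. The exact noncentral-t solution is 0.2089. Both round to 0.21; the table prints 0.29.
3. Variants: a one-sided α of 0.05 gives 0.185. Neither calculation gives 0.29 for this allocation. The printed value equals the 5%-row entry in the same column.
4. Power at the printed value: Φ(0.29/0.0745 − 1.960) = Φ(1.931) = 0.973. Power at 0.21 SD is 0.804.
5. The rest of the table: of the other 35 cells, 30 reproduce to the printed rounding. Five differ by about 0.01 SD: 25% and 75% exposed at N = 1,000 (0.205 against 0.21) and at N = 2,000 (0.145 against 0.15), and 5% exposed at N = 250 (0.816 against 0.83). The last is explained if 12 rather than 12.5 people are counted as exposed: 2.802 × √(1/12 + 1/238) = 0.829. These gaps have no practical effect.

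**Table 3**

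The stated chi-square calculation (pooled variance under the null, no continuity correction) reproduces the 144 cells with a mean relative difference of 0.2%. The largest is 3.0%, at N = 250 with 5% exposed and a 30% outcome. The table is sound, so the sentence can be tested against it.

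Printed minimum detectable odds ratios at N = 2,000, with those at or above 2.00 in bold:

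| Referent outcome | 5% exposed | 10% | 25% | 50% | 75% | 90% |
|---|---|---|---|---|---|---|
| 3% | **3.21** | **2.52** | **2.02** | 1.89 | **2.10** | **2.81** |
| 5% | **2.67** | **2.16** | 1.77 | 1.68 | 1.82 | **2.32** |
| 10% | **2.19** | 1.82 | 1.55 | 1.47 | 1.57 | 1.89 |
| 30% | 1.80 | 1.54 | 1.36 | 1.31 | 1.36 | 1.56 |

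Nine cells are bold. Six combine a 3% or 5% outcome with 5%, 10% or 90% exposed, and the exception covers those on a natural reading. At N = 5,000, only 3% with 5% exposed (2.27) and 3% with 90% exposed (2.00) reach 2.00, and both are covered too. Three cells remain: 3%/25% and 3%/75%, where the share is not extreme, and 10%/5%, where the outcome is not clearly rare.

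Power for an odds ratio of 2.00 in those three: p₁ = 2p₀/(1 + p₀), and power = Φ[(p₁ − p₀ − 1.960 × SE₀)/SE₁], with SE₀ pooled and SE₁ unpooled.

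| p₀ / exposed | n₁ : n₀ | p₁ | SE₀ | SE₁ | Power |
|---|---|---|---|---|---|
| 3% / 25% | 500 : 1,500 | 0.0583 | 0.00976 | 0.01136 | 0.79 |
| 3% / 75% | 1,500 : 500 | 0.0583 | 0.01138 | 0.00974 | 0.73 |
| 10% / 5% | 100 : 1,900 | 0.1818 | 0.03133 | 0.03918 | 0.70 |

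Solving the same expression for 80% power at an odds ratio of 2.00 gives N of about 2,062, 2,331 and 2,661.

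**The case against.** The strongest reply is that both items are editorial. The Table 4 slip is one cell of 36, probably typographical. It understates sensitivity, so nobody relying on it would plan too small a study. The conclusion about half a standard deviation is unaffected. The sentence after Table 3 is a summary with an explicit exception, its terms are loose, and the exact values stand directly above it. Of the three uncovered cells, 2.02 is a near miss. The study is a registry without narrow prior hypotheses, and no target is fixed here. All of this stands, and it sets the severity.

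It does not remove the errors. No reading of the stated method makes 0.29 right, and the printed 'and' does leave the three cells outside the exception.

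A reader might be tempted further, in three ways that the document does not support:

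- That Table 3 flatly contradicts the sentence because nine of 24 cells at N = 2,000 are at or above 2.00. That count ignores the exception, which covers six of them.
- That a team would stop at 2,000 and be underpowered. The protocol nowhere uses 2,000 as a target. Section 8.2 says that size will depend largely on the disaster, and the worked example in Appendix D assumes 100.
- That the tables are generally unreliable. Apart from the one cell, they reproduce closely.

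**Conclusion.** The point holds as a minor one. The Table 4 entry for 90% exposed at N = 2,000 should be 0.21 SD. The printed 0.29 is too large by 0.08 SD, about 40% (0.29/0.209 = 1.39), in the conservative direction. This rests only on the method and allocation stated in section 8.2.

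The sentence after Table 3 is imprecise rather than wrong throughout. Its exception leaves out three N = 2,000 scenarios, in which power for an odds ratio of 2.00 is 0.70 to 0.79 instead of at least 0.80. That rests on reading 'and' literally, on not calling 25% or 75% an extreme share, and on not calling a 10% outcome rare. No fixed sample size or confirmatory test depends on either item.

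**What to change.** 1. Table 4, 90% row, N = 2,000: change 0.29 to 0.21.
2. Sentence after Table 3, either of:
   - Replace 'and' by 'or' between the two conditions of the exception. This covers all three cells. It also exempts some that are in fact below 2.00, such as 3%/50% (1.89) and 30%/5% (1.80), so it is safe but coarse.
   - Preferably, limit the statement to the tabulated scenarios, for example: 'Among the scenarios in Table 3 at N = 2,000, the minimum detectable OR is below 2.00 for 30% outcomes at every exposure share shown, for 10% outcomes with 10–90% exposed, for 5% outcomes with 25–75% exposed, and for 3% outcomes only with 50% exposed.' This matches all 24 cells. The upper bound on exposure is needed: by the same method, a 10% outcome with 95% exposed gives 2.35.

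The cost is one number and one sentence at the next amendment. No design, procedure or analysis changes.

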9.1 Investigator Responsibilities

The Principal Investigator (PI) will:

- Submit the protocol, informed consent form, proposed recruitment materials, and any other materials for participants to the NIEHS IRB for review and approval, and ensure that participants are not enrolled until the submission has been approved in writing by the IRB
- Submit a written report to the IRB within 60 days of protocol implementation outlining response rates, evaluation of procedures, adverse events etc. (see Appendix F for full list of report elements)
- Obtain IRB approval of the annual Continuing Review for the duration of the study

- Obtain IRB approval for all amendments to the protocol, informed consent form, and other study documentation referenced above and ensure that amendments are not implemented without prior IRB approval
- Monitor and evaluate study progress, including periodic assessments of accrual, administration of informed consent, data quality, timeliness of data collection, participant risk versus benefit, performance of contractors, and other factors that can affect study outcomes (including external variables that may be related to the study, such as scientific findings that may have an impact on the safety of the participants or the ethics of the study)
- Track and appropriately report Unanticipated Problems (UPs), Protocol Deviations (PDs), Adverse Events (AEs), deaths, withdrawal of consent for sample storage, and early study termination, in accordance with NIEHS IRB policies and applicable NIH SOPs (e.g., NIH HRPP SOP 16 “Reporting Requirements for Unanticipated Problems, Adverse Events and Protocol Deviations”); in particular, the PI will report all Serious UPs, Serious PDs, and Serious AEs to the NIEHS IRB and NIEHS Clinical Director as soon as possible, but not more than 7 days after the PI first learns of the event.

9.2 Coordinating Center Responsibilities

Social & Scientific Systems, Inc. (SSS), a company that provides professional research services, will serve as the coordinating center and will function in a supportive and collaborative role through an existing contract with the NIEHS.

The coordinating center will be responsible for creating required study documents, conducting training, developing and implementing operational plans and study procedures, data management, study monitoring, and the performance of subcontractors who support ancillary research activities. Activities of the coordinating center will be conducted in collaboration with the PI and any relevant expert consultants.

Research study staff from the coordinating center will have the necessary education, qualifications, and experience to conduct all research study activities. Study staff will be required to undergo pre-employment screening and produce credentials commensurate with the anticipated level of complexity. After hire, they will receive training in human subjects’ protection, CPR, blood borne pathogens, data security, ethics, and study specific training modules including disaster specific health and safety training, informed consent administrations, procedural conduct, questionnaire administration, distressed participant training, and others. Training requirements and conduct are covered in the Field Operations Guide. Staff will be required to complete training programs specific to their roles in the project, pass proficiency testing, and receive certification prior to conducting study procedures. Our current intramural research team is led by personnel with previous disaster response experience including 9/11 in New York City, Hurricanes Katrina, Charlie and Wilma, pandemic influenza response,

HazMat response, and the GuLF STUDY. All study staff will be required to sign confidentiality agreements.

Data managers at the coordinating center will generate data Quality Control (QC) reports that will allow the study investigators and coordinating center staff to identify problems with missing, inconsistent, or otherwise implausible data so that any problems with data quality can be identified and corrected in a timely manner. In situations when completion of missing individual data is desired, the RAPIDD study team reserves the right to re-contact participants. All participants are informed of the possibility of follow-up during the consenting process.

Study managers at the coordinating center will monitor accrual and procedural completion data, review QC assessment forms quarterly, and coordinate site monitoring visits as part of the overall quality control process. Study managers will conduct periodic quality control assessments of staff performance using standardized quality control checklists and will provide feedback to staff. Corrective actions for unsatisfactory performance will include coaching, retraining, or termination. The PI will review unanticipated problems, adverse events, and protocol deviations as they occur, and they will also be reviewed in aggregate at least annually to identify any negative trends.

Study monitoring will occur in accordance with NIEHS requirements, and will be performed to ensure compliance with the protocol, NIEHS research policies, and federal regulations for the protection of human subjects (see [Section 10.1](#)).

9.3 Informed Consent Administration

The PI is responsible for ensuring informed consent is obtained from all participants and properly documented in compliance with 45 CFR 46.

A one-page consent form summary will be used to guide the informed consent process. To help potential participants make an informed decision about enrollment, the designated study staff, trained in informed consent administration, will discuss the study's purpose, duration of participation, procedures, risks, benefits, record confidentiality, how to contact study personnel, and the rights of participants. Potential participants will be given ample time to ask questions and obtain clarifications regarding the study prior to agreeing to enroll. Bilingual study staff will be available to work with non-English speaking participants for common foreign languages (e.g., Spanish) likely to be encountered. The study team may also use remote interpreter services in order to effectively communicate with non-English speakers so they can make an informed decision about participation.

After voluntarily agreeing to take part in the study, participants will be asked to sign and date a current IRB-approved informed consent form (ICF), and will be given a copy of the signed and dated document. The signed ICF will be obtained prior to the initiation of any study procedures. Participants will be informed that they may withdraw consent at any time throughout the study. Participants will also be informed that they may be contacted by future researchers for follow-up studies and that participation in follow-up studies is completely voluntary and will

not affect their participation in this protocol. The consent form will contain contact information for coordinating center staff and the NIEHS IRB in the event that questions or concerns emerge after the visit. The original version of the ICF will be retained in the study files. Random review of consent forms will be included in the study's clinical monitoring plan ([Section 10.1](#)).

Participants will be informed of any changes in the design or risks of the study that could impact the participant (e.g., a change in the risk for breach of confidentiality).

9.4 Evaluation of Risks/Discomforts and Benefits Ratio

9.4.1 Potential Benefits

Participation in this study is not anticipated to provide any direct benefit to a participant's overall health or any existing medical conditions.

Study participants may benefit from the positive feelings associated with participating in a study that explores the health effects of a disaster that may add value to their community. The knowledge gained from this study may have a significant impact on future public health responses to disasters. It is also possible that participants may benefit directly from public health responses that are based on early findings from research conducted using samples and data collected during this study. Additionally, participants may benefit from receiving the results from the registry exam which they can share with their physician or healthcare provider.

9.4.2 Potential Risks

The proposed study presents minimal risk to participants. Adverse events associated with study procedures are expected to be uncommon and limited to mild and transient discomforts. In order to minimize risks to participants, qualified, experienced, and well-trained research staff will conduct all study procedures. Possible known risks are described in the following sub-sections.

